8.4.3 Demographic and Baseline Characteristics

Demographic characteristics (including age, sex at birth, ethnicity, and race) and baseline characteristics (including height, weight, body mass index (derived in eCRF), and disease characteristics) will be presented descriptively.

8.4.4 Pharmacodynamic Analyses

The assessment of cytokine PD parameters will be described and provided in a separate report(s).

Page 54 of 71

8.4.5 Handling of Missing Values

Missing data will not be imputed for the safety summaries or the efficacy summaries conducted on the PP population.

For efficacy summaries conducted on the ITT population a model based multiple imputation procedure will be used to impute missing data, where appropriate. Rules for imputation of missing efficacy data will be detailed in the SAP.

Patients who prematurely discontinue the study will be evaluated based on the data collected at each visit attended. Data collected during the withdrawal visit will be used as an end of study assessment for these patients. If the withdrawal visit was performed >1 day after the last dose was administered, then the previous visit will be used as the end of study assessment.

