3.2 Discussion of Study Design

The study is designed to assess the safety, tolerability, efficacy, PK, and PD of ATI-450 in patients with CAPS.

Many patients with CAPS achieve complete or near complete disease remission with currently available anti-IL-1 therapies. Therefore, the study is designed to minimize patient's time off anti-IL-1 therapy due to potentially harmful long-term complications that can result from prolonged relapse of disease symptoms.

The study is open-label and there is no washout period for anti-IL-1 therapy; patients enrolled in the trial will begin treatment with study medication (Day 1) on the day of their next scheduled dose of anti-IL-1 therapy. At the end of the 12-week treatment period, ATI-450 administration will be discontinued, and patients will delay administration of anti-IL-1 therapy until 7 days (+4 days) after the last dose of ATI-450.

The 12-week treatment period was selected to allow sufficient time to explore the efficacy of ATI-450 in maintaining disease remission, and to adequately rule out the potential for prolonged disease remission caused by the last dose of anti-IL-1 therapy. Due to its long $t_{1/2}$, this is particularly relevant in instances when canakinumab is used.

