4.4.2 Premature Discontinuation from the Study

Participation in the study is strictly voluntary. A patient has the right to withdraw from the study at any time for any reason, without any reprisal.

The investigator has the right to terminate participation of a patient for any of the following reasons:

- Difficulties in obtaining blood samples
- Violation of the protocol
- Any other reason relating to integrity of the study data

If a patient is withdrawn from the study, the study monitor/sponsor will be informed immediately. If there is a medical reason for withdrawal, the patient will remain under the supervision of the investigator until satisfactory health has returned.

If the patient withdraws consent for disclosure of further information, the sponsor may retain and continue to use any collected data before such a withdrawal of consent. If a patient withdraws from the study, he/she may request destruction of any samples taken and not tested, and the investigator must document this in the site study records.

Although a patient is not obliged to give his/her reason(s) for withdrawing prematurely from a study, the investigator should make a reasonable effort to ascertain the reason(s), while fully respecting the patient's rights.

At the time of premature study discontinuation, the investigator should make every effort to ensure the patient completes the assessments indicated at the end of study (Day 84) and safety follow-up visit (Day 7); see Table 1.

Patients who prematurely discontinue from the study cannot subsequently rejoin the study. For details on the discontinuation of study sites or the study as a whole, see Section 14.

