5.1.1 Medical History

Relevant medical history and current medical condition, including CAPS disease phenotype and duration as well as date of first diagnosis and previous treatments including any previous biologic or non-biologic therapy for CAPS will be recorded in the eCRF.

At the baseline visit, inclusion/exclusion criteria will be reviewed and updated to ensure the patient remains qualified for the study. Findings that are observed after the patient has signed the Informed Consent Form (ICF) and prior to the first dose of ATI-450 will be recorded as medical history on the eCRF. Any adverse event observed after the patient has signed the ICF that meets the definition of a SAE (See Section 7.1.2), in which case, all applicable safety reporting procedures will be followed by the site.

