5.2.1.2 Time to Relapse

Time to relapse will be assessed during the treatment period. Relapse is defined as a two-point worsening on the PGA scale.

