8.2 Analysis Populations

- The ITT population will include all patients who have been administered at least one dose of study medication.
- The PP population will include all patients who complete 12-weeks of treatment and 4-weeks of follow up and have completed assessments.

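### Section 8.4.5 replaces a late withdrawal visit with the previous visit and makes no exception for relapse, so if that value fills Day 84, an ITT patient who relapses and stops can be scored as in remission

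*Combined protocol and SAP*

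**What the plan says.** Section 8.4.5 holds three rules that can all apply to the same early leaver.

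- Attended visits: "Patients who prematurely discontinue the study will be evaluated based on the data collected at each visit attended".
- Withdrawal visit: its data serve as the end of study assessment. However, "If the withdrawal visit was performed >1 day after the last dose was administered, then the previous visit will be used" in that role. No exception for relapse or loss of remission is given there or elsewhere.
- Imputation: "For efficacy summaries conducted on the ITT population a model based multiple imputation procedure will be used to impute missing data, where appropriate". The imputation rules are left to the SAP, and the supplied text contains no separate SAP.

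The section does not say which rule comes first.

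On populations, Section 8.2 states: "The ITT population will include all patients who have been administered at least one dose of study medication". The per-protocol set requires 12 completed weeks of treatment, so early leavers count only in ITT. Section 8.4.1 reports clinical and disease remission over time in both sets.

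On relapse, Section 5.2.1.2 defines it as a two-point PGA worsening and says: "Time to relapse will be assessed during the treatment period". It is silent on visits made after the last dose.

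On early exit, Section 4.4.2 says: "At the time of premature study discontinuation, the investigator should make every effort to ensure the patient completes the assessments" scheduled for Day 84 and the Day 7 follow-up. It sets no limit in days from the last dose.

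**The concern.** Patients enter in remission, so the event that carries the efficacy information is loss of remission. A patient who relapses has good reason to stop. Section 4.4.1 does not list relapse among its stopping reasons, but Section 3.2 warns of "potentially harmful long-term complications that can result from prolonged relapse of disease symptoms", and Section 4.4.2 lets a patient leave for any reason. If that patient is seen two or more days after the last dose, the visit that documents the relapse is set aside, and the visit that replaces it may predate the relapse. A failure to maintain remission could then be reported as remission maintained.

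This also cuts against the design rationale. Section 3.2 justifies 12 weeks partly by the need to rule out remission carried over from the last anti-IL-1 dose. Taking Day 1 or an early visit as the end of study value can bring that carry-over back into the result.

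**Working it through.** The plan gives no remission, relapse or dropout rate to reproduce. Section 8.3 sets N at up to 10 on feasibility grounds. The check is therefore one of logic, followed by simple arithmetic.

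**1. Is every relapse outside remission?** The PGA runs absent, minimal, mild, moderate, severe (Section 5.2.1). Entry requires minimal or better (Section 4.1, criterion 2). Two points worse than absent is mild or worse, and two points worse than minimal is moderate or worse. Clinical remission is absent or minimal, so every relapse is non-remission.

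**2. How old can the substitute be?** PGA is rated at visits on nominal Days 1, 14, 28, 56 and 84 (Table 1). The gaps are 13, 14, 28 and 28 days, so the previous visit can be about four weeks earlier, or more if a visit was missed.

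**3. Stop before Day 14 with no other visit attended.** The previous visit is Day 1.
- Its assessments are taken before the first dose (Table 1, footnote 2), and they are the baseline (Section 8.1).
- Section 5.1.1 says: "At the baseline visit, inclusion/exclusion criteria will be reviewed and updated to ensure the patient remains qualified for the study". PGA is therefore minimal or better, and clinical remission is met.
- Disease remission also needs hsCRP and SAA at or below 10 mg/L or within 30 percent of baseline (Section 5.2.1.1). Baseline differs from itself by 0 percent, so this is met at any level.
- Change from baseline is zero.

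Under substitution this patient is in remission on both definitions, from data collected before any ATI-450.

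**4. Size.** Each such patient shifts the ITT proportion by 100/N points: 10 at N=10, 12.5 at N=8, 16.7 at N=6.

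Take N=10 with one such patient and x of the other nine in remission. Substitution gives (x+1)/10, and counting the relapse gives x/10. The values of x are assumed. Intervals are exact (Clopper-Pearson) 95%.

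| x | Substitution | Relapse counted |
|---|---|---|
| 9 | 10/10 = 100% (69.2 to 100) | 9/10 = 90% (55.5 to 99.7) |
| 8 | 9/10 = 90% (55.5 to 99.7) | 8/10 = 80% (44.4 to 97.5) |
| 7 | 8/10 = 80% (44.4 to 97.5) | 7/10 = 70% (34.8 to 93.3) |

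**5. What the one-day limit protects against.** Section 1.1.3 gives a half-life of about 9 to 11 hours. The fraction of drug remaining is 0.5^(t / half-life). At 24 h it is 15.7% to 22.0%, and at 48 h it is 2.5% to 4.9%. A visit two or more days after the last dose is therefore close to an off-drug observation.

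**The case against.** Four objections have force.

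- **The rule has a legitimate aim.** It separates status on ATI-450 from flare after stopping. Step 5 supports it: at a late visit the two cannot be told apart cleanly. The protocol measures off-drug symptoms separately (Section 5.2.2.1). This stands. It is a reason to keep the treatment-period window in the main time-to-relapse analysis, but it does not justify scoring the patient as in remission.
- **The effect depends on one reading.** Remission is reported over time, and no endpoint is named an end of study proportion. Table 1 labels Day 84 as end of study, which makes the reading natural, but no sentence says that the substituted assessment enters the Day 84 summary. The attended-visits rule may keep the late visit in other summaries. This stands as a condition on the point.
- **The SAP may settle the order.** Section 8.4.5 defers imputation rules to it. That deferral does not plainly reach the substitution rule, which is stated outright.
- **Several things must coincide.** These are relapse between visits, exit, a visit more than one day after the last dose, and a previous visit in remission. This also stands, and no frequency can be derived.

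A reader might infer that multiple imputation would correct the score, or that it would reproduce the inflated one. Neither follows. The result depends on whether the model sees the relapse visit and on its covariates, and the documents state neither.

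**Conclusion.** The gap is real, but conditional. As written, the substitution rule can turn a documented relapse into remission at end of study. For a stop before Day 14 with no other visit attended, it does so by construction. This holds only if the substituted value is used for the Day 84 ITT summary, which Section 8.4.5 leaves open.

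Each affected patient is worth 100/N points, or 10 at N=10. That is visible in a set this small, although well inside the exact intervals. Efficacy is descriptive and not primary (exploratory in the synopsis, secondary in Table 2). What is affected is how the result reads, not a formal test.

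A reader might go further and conclude that the reported remission proportion will be inflated. The documents do not support that. They give no rates of relapse, stopping or late visits, and the rule can also discard improvement seen after anti-IL-1 therapy is restarted, so its bias is not always upward. It should be fixed because the wording permits the error and the correction is cheap.

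**What to change.** Amend Section 8.4.5, and carry the wording into the SAP.

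1. Never use a visit before the first dose as an end of study value, for any endpoint.
2. In the ITT remission proportions, count a patient who stops ATI-450 for relapse or lack of efficacy as not in remission from that point through Day 84. This comes ahead of previous-visit substitution and multiple imputation.
3. For other or unexplained stops, use a withdrawal visit within one day of the last dose, as already stated, and otherwise the planned multiple imputation. Add a sensitivity analysis counting these stops as non-remission. A restart of anti-IL-1 therapy after a stop unrelated to disease activity is not by itself a failure in the main analysis. An example is a stop for a positive Day 1 SARS-CoV-2 swab (Section 5.1.5).
4. Keep the treatment-period window for time to relapse. In a sensitivity analysis, count a relapse recorded at a late withdrawal visit as an event, flagged by days since the last dose.
5. State how the Section 8.4.5 rules rank for each ITT endpoint.

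The cost is protocol and SAP wording, one recorded reason-for-stopping category (relapse or lack of efficacy), a little more analysis, and a possibly lower remission figure. Section 4.4.2 lets patients withhold their reason, so some stops for relapse will be unexplained and will show only in the item 3 sensitivity analysis.

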5.1.5 COVID-19 Monitoring

At Baseline Visit 2, all patients entering the treatment phase of the study must have a nasopharyngeal (preferred) or oropharyngeal swab collected prior to the first dose of ATI-450 to test for the presence of the SARS-CoV-2 virus. The sample will be sent to the study's central lab for analysis by reverse transcription polymerase chain reaction (RT-PCR) with results reported as either 'Detected' or 'Not detected' for SARS-CoV-2 viral particles. If central laboratory testing cannot be performed at the time of Baseline Visit 2 (i.e., lab supplies are not yet available) and the study site is able to perform equivalent testing locally, they may choose to do so, as long as the test results are available in the patient's research chart for sponsor review. Patients should not initiate ATI-450 in the absence of central laboratory or locally equivalent testing being performed.

Patients are allowed to dose with ATI-450 in the interval between sample collection at Baseline Visit 2 and result reporting as long as there is no clinical suspicion of COVID-19 infection or recent exposure of the patient to an individual with a confirmed, active infection.

If the patient's results are positive for SARS-CoV-2 following sample collection at Visit 2, the patient will need to be notified immediately upon receipt of the results and treatment with ATI-450 will be permanently discontinued. The patient should be advised to begin self-isolation and self-monitoring procedures according to any applicable local, state, and/or federal health recommendations. Referral to an appropriate health care provider for management of the patient's COVID-19 diagnosis should also be made. The patient should be seen for the safety follow-up Visit 7 (see Table 1) only at such time that the investigator assesses the risk for incidental transmission from viral shedding to be minimized. The patient's COVID-19 diagnosis will be reported as medical history unless the patient's clinical course progresses such that criterion for SAE reporting is met (See Section 7.1.2), in which case, all applicable safety reporting procedures will be followed by the site.

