8 STATISTICS

8.1 General Procedures

Analyses will be performed using SAS® (SAS Institute, Cary, NC, US) by the sponsor or its representatives.

The statistical analysis plan (SAP) will be approved prior to any lock of the study database and unblinding of the study data. The SAP will provide a detailed description of the statistical methods and expand on the details provided in the protocol.

Descriptive statistics (number of observations, mean, standard deviation, median, minimum, and maximum) will be provided for continuous variables, and counts and percentages will be presented for categorical variables.

Baseline is defined as the last non-missing measurement before or on the date of first administration of study medication.

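### Section 8.4.5 lets the pre-dose baseline visit stand as the end-of-study result for an ITT patient who withdraws before Day 14 and is assessed more than 1 day after the last dose

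*Combined protocol and SAP*

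**What the plan says.** Section 8.4.5 gives two steps for patients who leave the study early. The default is: "Data collected during the withdrawal visit will be used as an end of study assessment for these patients". The exception is that where this "visit was performed >1 day after the last dose was administered, then the previous visit will be used as the end of study assessment". Nothing restricts which visit can be the previous one, and the section does not define the withdrawal visit.

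The same section also says: "For efficacy summaries conducted on the ITT population a model based multiple imputation procedure will be used to impute missing data, where appropriate". It leaves the imputation rules to the SAP and does not say whether imputation or previous-visit substitution takes precedence.

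The other relevant provisions are:

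- Section 8.1: "Baseline is defined as the last non-missing measurement before or on the date of first administration of study medication".
- Section 8.2: one dose is enough for ITT, whereas PP requires completion of treatment and follow-up.
- Table 1 and section 3.1: the first clinic visit after Visit 2 (Day 1) is Visit 3 (Day 14, with a 1-day window either way). Footnote 2 of Table 1 puts PGA, KSS and laboratory sampling before dosing on dosing days.
- Section 4.1: entry requires a PGA of minimal or better, attributed to anti-IL-1 therapy. Section 5.1.1 adds: "At the baseline visit, inclusion/exclusion criteria will be reviewed and updated to ensure the patient remains qualified for the study".
- Section 5.2.1.1: clinical remission is a PGA of absent or minimal. Disease remission also needs hsCRP and SAA that are normal (10 mg/L or lower) or within 30 percent of baseline. Both are to be assessed during the treatment period.

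**The concern.** Replacing a late off-drug assessment with an earlier on-drug one is reasonable. The rule as written goes further, because the earlier visit may precede the first dose. The end-of-study result then describes the patient on prior anti-IL-1 therapy and says nothing about ATI-450. Section 3.2 gives as one reason for the 12-week treatment period the need to rule out remission that lingers from the last anti-IL-1 dose. Carrying the Visit 2 value forward counts exactly that carried-over remission as a success.

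The stake is the end-of-study ITT remission proportion in a set of about 10, where one patient is a visible share. The change from baseline in PGA, hsCRP and SAA also receives a zero that was not observed on drug.

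**Working it through.** The only planned figure here is the sample size of up to 10 (section 8.3). It rests on feasibility, so there is no calculation to reproduce. The check has two parts.

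**1. What the rule returns.** Take a patient who has at least one dose, leaves the study before Visit 3, has no assessment within 1 day of the last dose, and attends no other visit before the withdrawal visit.

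- Population: ITT (one dose), not PP.
- Previous visit: Visit 2, measured before dosing. Under section 8.1 this is normally also the baseline.
- PGA: absent or minimal by the entry criterion, so clinical remission is met and the change is 0.
- hsCRP and SAA: each is compared with itself, so the change is 0% and the 30 percent condition is met. This holds for a normal pair such as 3 and 4 mg/L and for an elevated pair such as 25 and 40 mg/L.
- Result: clinical remission, disease remission and zero change, whatever the withdrawal visit showed.

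**2. Effect on the proportion.** Let k be the number in remission at end of study among the other patients.

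One such patient in 10, rule against observed cases:

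(k+1)/10 − k/9 = (9−k)/90

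For k = 0 to 9 this is 10.0, 8.9, 7.8, 6.7, 5.6, 4.4, 3.3, 2.2, 1.1 and 0 percentage points.

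One such patient in 10, rule against true status if that patient had relapsed:

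(k+1)/10 − k/10 = 1/10, or 10 points for every k

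At k=7 the rule gives 8/10 = 80% (Clopper-Pearson 95% interval 44.4 to 97.5) and true status gives 7/10 = 70% (34.8 to 93.3).

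Two such patients in 10, rule against observed cases:

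(k+2)/10 − k/8 = (8−k)/40, which is 20, 10, 5 and 0 points at k = 0, 4, 6 and 8

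One such patient, replaced as section 4.4.1 allows, so that 11 are dosed:

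(k+1)/11 − k/10 = (10−k)/110, which is 9.1, 6.4, 4.5 and 2.7 points at k = 0, 3, 5 and 7

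**How often.** The documents give no rate. Under assumed rates of 1%, 3% and 5% per patient, independent across patients, the chance of at least one case in 10 is 1 − 0.99^10 = 9.6%, 1 − 0.97^10 = 26.3% and 1 − 0.95^10 = 40.1%. These rates are illustrations only.

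**The case against.** **The rule has a sound purpose.** Section 1.1.3 gives a half-life of about 9 to 11 hours. At 24 hours 0.5^(24/9) = 16% to 0.5^(24/11) = 22% of the drug remains, so a later visit is increasingly off drug. This stands, and it supports falling back to an earlier on-treatment visit. It does not support falling back to a visit before any drug was taken.

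**The conditions are narrow.** Section 4.4.2 asks for the Day 84 and Day 7 follow-up assessments when a patient leaves the study. If the Day 84 set is done within 1 day of the last dose, its observed values are used. If it is done later but as a separate visit before the one treated as the withdrawal visit, then the previous visit is post-baseline. Both limits stand. A reader might infer that every stop before Day 14 becomes a remission; the text does not support that.

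**The COVID-19 provision is not a clear example.** Section 5.1.5 says "Patients are allowed to dose with ATI-450 in the interval between sample collection at Baseline Visit 2 and result reporting". A positive result then ends treatment, and the next visit may be delayed. A reader might take this as a certain trigger. However, it describes stopping the drug and attending safety follow-up, while the rule covers patients who leave the study, and sections 4.4.1 and 4.4.2 keep the two apart. It is a possible route only.

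**Imputation and the SAP may cover it.** Multiple imputation applies to missing data, and the substitution supplies a value, so nothing need be left to impute. The imputation rules are deferred to the SAP, but the substitution is stated outright. The SAP can still correct it.

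**Little depends on it.** The primary objective is safety, and the efficacy summaries are descriptive. This stands and sets the severity.

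**Conclusion.** The rule is wrong as written, and the point is minor. Under the stated conditions, section 8.4.5 scores a patient as in remission with zero change from a pre-dose value. With one such patient in 10, the end-of-study ITT proportion rises by (9−k)/90 over the observed-case figure, between 0 and 10.0 points, or by 10 points over true status if that patient had relapsed. The rule never lowers the proportion below the observed-case figure. It is right for that patient only if the patient happened still to be in remission.

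This assumes that the withdrawal visit means the first assessment after the patient leaves, and that the Visit 2 values are present. The frequency is unknown. PP, the Day 14, 28 and 56 summaries and time to relapse are unaffected. Weekly mean KSS comes from the daily diary, which the visit rule does not clearly govern.

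Two stronger readings are not supported. A reader might expect the remission curve to rise artificially between Day 56 and end of study, but that would compare observed cases with a substituted value, whereas imputation is planned for ITT at the earlier visits. A reader might also expect the hsCRP and SAA medians to be biased in the drug's favour. An added 0% can only leave the median percent change where it is or move it toward zero, so the direction of any benefit depends on the other patients.

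**What to change.** Add to section 8.4.5 or to the SAP:

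- The previous visit means the last post-baseline visit held on treatment or within 1 day of the last dose. A pre-dose visit is never the end-of-study assessment.
- Where no such visit exists, baseline is not carried forward. The end-of-study value is missing and follows the ITT missing-data rule in the SAP.
- The observed-case proportion with its denominator, and the actual withdrawal-visit value, are shown beside the ITT result.
- The withdrawal visit is defined, including whether it covers patients who stop the drug but attend follow-up.

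The choice between multiple imputation and scoring as not in remission belongs in the SAP, since neither is clearly better. Imputing a patient with no on-treatment data from at most 9 others is weak. Scoring as not in remission differs from observed cases by k/10 − k/9 = −k/90. At k=5 that is −5.6 points, against +4.4 under the present rule.

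The cost is a few sentences, slightly more reporting and a possibly less favourable end-of-study proportion. No visit, sample or patient is added, and section 8.1 places SAP approval before database lock.
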